### Clinical Laboratory Data Analysis

- All clinical laboratory abnormalities will be analyzed by participant and will include onset time and duration.
- Any clinically significant deviations in routine laboratory test results, will be reported as unsolicited AEs if they are considered clinically relevant by the investigator.

### Efficacy outcome analyses

- Pfs48/45-6C and R0.6C antibody prevalence and density will be determined by ELISA; the mean of duplicate concentration estimates is used for analyses. Antibody density will be expressed in  $\mu\text{g/mL}$  using humanized monoclonal antibody TB31F as a reference/standard. (Endpoint 5, 7 and 11).
- The R0 antibody prevalence and density will be determined by ELISA; the mean of duplicate concentration estimates is used for analyses. Antibody density will be expressed in  $\mu\text{g/mL}$  using R0 monoclonal antibody as a reference/standard. Alternatively, R0 antibody densities may be expressed in arbitrary units (AU) or R0 antibody densities may be estimated by subtracting measured R0 antibody levels from R0.6C antibody levels. (Endpoint 8).
- Pfs48/45-6C antibody density will be plotted over time per individual and either as a mean or geometric mean per group. AUC and mixed effects models may be used to investigate the effect of timepoints, dose/adjuvant group and their interactions on the 6C antibody concentration. Mixed models use specific random intercepts to control for the correlation within individuals (Endpoint 7).

- TRA will be quantified as the relative reduction in oocyst intensity for test samples (one feeder per test sample) compared to baseline serum controls. Samples may be tested in one or two independent SMFA experiments. If significant transmission reduction is measured, TRA values for each participant and time-point will be estimated using generalized linear models, as previously described. (Endpoint 2, 4 and 10).
- We may calculate the percentage of individuals per group that have at least 50%, 80% and 90% TRA at relevant timepoints and the percentage of individuals per group with statistically significant TRA at relevant timepoints. Mean TRA levels may also be calculated per study group per time point and compared between groups. (Endpoint 10).
- Modeled TRA estimates (based on antibody concentration) may be plotted against observed TRA estimates.
- TBA will be quantified as the reduction in oocyst prevalence in the presence of test serum as compared to (pooled) baseline serum^1 and presented per group and time-point. (Endpoint 6).

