2.1.2 Rationale

The renewed focus on malaria elimination has increased the priority of research towards development of interventions to block malaria transmission [10, 11]. By interrupting transmission of malaria parasites in mosquito vectors, a reduction in the number of secondary infections in the community is expected with an overall reduction in disease and mortality[12].

The lead TBV candidate R0.6C has shown good transmission reducing efficacy in rodent models. Also, a monoclonal antibody TB31F against the same PfS48/46 6C region has shown excellent safety and transmission reducing activity in humans in a recent clinical trial (van der Boor et al, manuscript in preparation). Efficacious TBVs would be a critical step on

the path towards malaria elimination and their safety and preliminary efficacy data can be acquired in malaria-naïve volunteers.

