7.3 Summary of findings from clinical studies

There is no past human experiences with the R0.6C/AIOH and R0.6C/AIOH + Matrix-M vaccines. However, the GLURP-R0 region, which constitute 76.7% of R0.6C, forms part of the malaria vaccine candidate, GMZ2, which has been tested in both European and African clinical trials listed in Table 3. Notably, GMZ2, adjuvanted with aluminum hydroxide (GMZ2/AIOH) was tested in 880 children 12-60 month of age in Burkina Faso (Banfora; n=580, Sapone; n=300).

To date 994 individuals, of whom the majority are African children below 5 years of age, have been immunized with GMZ2/AIOH. The GMZ2/AIOH formulation has shown excellent safety and tolerability confirming the safety of the expression system and the safety of the GLURP-R0 portion of R0.6C.

Table 3: Clinical experience of GMZ2/AIOH.

Trial registration number (Reference)	Title	Interventions	Characteristics	Population
NCT00397449 [14]	Safety and immunogenicity of GMZ2 - a MSP3-GLURP fusion protein malaria vaccine candidate	Biological: 
 • 10µ GMZ2/AIOH • 30µ GMZ2/AIOH • 100µg GMZ2/AIOH 	Phase 1a	30 healthy malaria-naïve German adults; 10 / group
NCT00424944 [14]	Safety and immunogenicity of the malaria vaccine candidate GMZ2 in malaria-exposed,	Biological: 
 • 100µg GMZ2/AIOH • VerorabTM 	Phase 1b	40 healthy malaria-exposed Gabonese adults; 20 / group

	adult individuals from Lambaréné, Gabon			
NCT00703066 [15]	A Randomized Controlled Phase Ib Trial of the Malaria Vaccine Candidate GMZ2 in African Children	Biological: 
• 30μ GMZ2/AIOH• 100μ GMZ2/AIOH• VerorabTM	Phase 1b	30 healthy malaria-exposed Gabonese children one to five years of age; 10 / group
PACTR201006 0002033537 [16]	A phase 2b randomized, controlled trial of the efficacy of the GMZ2 malaria vaccine in African children	Biological: 
• 100μ GMZ2/AIOH• VerorabTM	Phase 2b	1735 healthy malaria-exposed Gabonese children received three doses of vaccine (868 GMZ2, 867 control-vaccine).

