#### Exploratory Endpoints:

- 6) The functional TBA in the SMFA of volunteer sera collected at different time points compared to baseline (I1-1) in each of the four dose-adjuvant combinations.
- 7) The anti-6C antibody decay rate following R0.6C immunization for each of the four dose-adjuvant combinations.
- 8) The anti R0.6C and anti-R0 antibody quantity in volunteer sera collected at different time points in each of the four dose-adjuvant combinations.
- 9) The cellular immune responses in volunteers samples collected at different time points in each of the four dose-adjuvant combinations.
- 10) The difference in TRA between the two dose groups (30 or 100 $\mu$ g R0.6C) and/or between adjuvant groups (alhydrogel and alhydrogel+Matrix-M).
- 11) The difference in peak anti-6C antibody quantity between the two dose groups (30 or 100 $\mu$ g R0.6C) and/or between adjuvant groups (alhydrogel and alhydrogel+Matrix-M).

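### The SAP expresses anti-R0.6C in µg/mL against an antibody to the 6C part only, and its option to derive anti-R0 by subtraction is wrong as written

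*SAP*

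**What the plan says.** The first ELISA bullet under Efficacy outcome analyses in the SAP covers two antigens: "Pfs48/45-6C and R0.6C antibody prevalence and density will be determined by ELISA". It then gives a single unit and a single standard, µg/mL "using humanized monoclonal antibody TB31F as a reference/standard. (Endpoint 5, 7 and 11". In the SAP's numbering those three endpoints are all anti-6C: quantity over time, decay rate, and peak difference between groups.

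The second bullet deals with R0. Its unit is µg/mL "using R0 monoclonal antibody as a reference/standard", with arbitrary units as one alternative. A further alternative reads: "R0 antibody densities may be estimated by subtracting measured R0 antibody levels from R0.6C antibody levels". This bullet alone is tagged to Endpoint 8, which is defined as "The anti R0.6C and anti-R0 antibody quantity in volunteer sera collected at different time points in each of the four dose-adjuvant combinations".

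Both bullets treat the results as concentrations: "the mean of duplicate concentration estimates is used for analyses".

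On specificity, protocol section 2.1.2 describes "a monoclonal antibody TB31F against the same PfS48/46 6C region". Section 7.3 refers to "the GLURP-R0 region, which constitute 76.7% of R0.6C". The Statistical Software section of the SAP also names R0.6C antibody kinetics for non-compartmental analysis.

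**The concern.** An ELISA standard converts signal to mass for antibodies that behave like the standard. TB31F can do this for antibody to 6C. On an R0.6C plate the signal also comes from antibody to R0, and a 6C-specific standard says nothing about the signal per µg of that part. The plan itself expects a response to R0, since Endpoint 8 measures it.

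Two things are at stake. First, anti-R0.6C would be tabulated in the same unit as anti-6C and anti-R0, inviting a reader to compare the columns and judge how much of the response goes to the carrier R0. The scales do not support that. Second, the SAP permits arithmetic across the scales, and the formula it gives does not estimate the quantity it names.

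There is also a gap in the endpoint tags. Anti-R0.6C is named first in Endpoint 8, but the bullet that says how it is measured is tagged only to anti-6C endpoints.

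**Working it through.** The plan states no figure for this point, so there is none to reproduce. The passages settle the structure; the arithmetic only shows scale.

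**The assays side by side**

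| Assay | Standard | Standard binds | What the plate can capture |
|---|---|---|---|
| 6C | TB31F | 6C | anti-6C |
| R0.6C | TB31F | 6C | anti-6C and anti-R0 |
| R0 | R0 monoclonal, or arbitrary units | R0 | anti-R0 |

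Standard and antigen match in the first and third rows but not in the second. The SAP gives no bridging factor or parallelism check, and does not label anti-R0.6C as TB31F-equivalent.

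**Illustrative model (assumptions, not document figures).** Let a be true anti-6C and b true anti-R0, in µg/mL, each reading 1:1 against its own monoclonal. Let r be the signal per µg of anti-R0 relative to TB31F on the R0.6C plate. The documents do not give r; the range 0.25 to 4 is assumed, as is a linear signal.

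Reported R0.6C = a + r·b. This equals the true total a + b only at r = 1.

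With a true total of 100:

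| Anti-R0 share | r = 0.25 | r = 1 | r = 4 |
|---|---|---|---|
| 50% (a = 50, b = 50) | 62.5 | 100 | 250 |
| 76.7% (a = 23.3, b = 76.7) | 42.5 | 100 | 330.1 |

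The 76.7% is a share of the protein, used here only as an example of an antibody share.

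**The subtraction as written.** R0.6C − R0 = (a + r·b) − b = a + (r − 1)·b.

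- At r = 1 this is a, which is anti-6C and not anti-R0.
- With a = 23.3 and b = 76.7, it gives 42.5 − 76.7 = −34.2 at r = 0.25, 23.3 at r = 1, and 330.1 − 76.7 = 253.4 at r = 4. The anti-R0 it is meant to estimate is 76.7.
- It equals b only when a = (2 − r)·b, for example in an even mix at r = 1. That is coincidence.
- It also needs a measured R0 value as input, so it cannot replace that measurement.

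**If subtracting 6C was intended.** R0.6C − 6C = r·b. For b = 76.7 this runs from 0.25 × 76.7 = 19.2 to 4 × 76.7 = 306.8. Correcting the slip alone would not recover anti-R0 in mass units.

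**Ratios within the R0.6C assay.** If anti-6C and anti-R0 both double, the ratio is 2.0 at any r. If only anti-6C doubles (10 to 20, anti-R0 constant at 30), the true ratio is 50/40 = 1.25. The reported ratio is 27.5/17.5 = 1.57 at r = 0.25 and 140/130 = 1.08 at r = 4. Dividing every reading by a fixed pooled serum leaves these ratios unchanged, because the divisor cancels.

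**The case against.** The strongest reply has four parts.

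- **The reference is named openly.** A reader can see that the value is relative to TB31F, and protocol section 8.3.14 speaks of anti-R0.6C titres, which are relative measures. This limits the harm. The SAP still calls the results concentration estimates and prints no equivalent-unit label.
- **The tags may limit the scope.** Since the TB31F sentence is tagged only to anti-6C endpoints, it could be read as leaving the R0.6C standard unspecified. That is possible, although the bullet names both antigens. On that reading anti-R0.6C under Endpoint 8 has no stated standard, and the text still needs correcting.
- **The size is invented.** The relative signal, the linearity and the antibody mixes are not in the documents, and giving polyclonal anti-6C a 1:1 reading against one monoclonal is itself an assumption. This stands. No numerical bias can be attributed to the trial.
- **Little depends on it.** Endpoint 8 is exploratory and is described within each arm. The planned between-group antibody comparison, Endpoint 11, is anti-6C. This also stands.

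A reader might infer that anti-R0.6C cannot be compared with anti-6C at all. The documents do not support that: both are given the same TB31F standard, so the most that can be said is that they are not shown to be comparable as mass. Nor do they support a claim that a planned between-arm result is biased, because no between-arm comparison of anti-R0.6C is specified.

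None of these replies rescues the subtraction.

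**Conclusion.** The point holds as a minor one, wrong as written in one place. The subtraction crosses two standards and uses R0 to obtain R0; at equal signal per µg it returns anti-6C. That conclusion needs no assumed bias. The anti-R0.6C unit is a labelling fault: the value is a TB31F-equivalent, not shown to be a mass concentration and not on the anti-R0 scale.

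The reach is narrow: exploratory Endpoint 8, and the R0.6C kinetics so far as they are run on anti-R0.6C values. TRA and the anti-6C endpoints (5, 7 and 11) are untouched by this mismatch. Anti-R0.6C values remain usable as relative values over time or between arms, provided it is said that ratios shift when the R0:6C mix changes. The numerical ranges in the working rest on an assumed relative signal and assumed mixes, and show only what could happen.

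**What to change.** Change the SAP wording as follows:

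1. Limit µg/mL against TB31F to the 6C ELISA, tagged to Endpoints 5, 7 and 11 as now.
2. Move anti-R0.6C to Endpoint 8 and report it as TB31F-equivalents, labelled as such, or in arbitrary units. Apply the same label to any kinetics run on it.
3. Delete the subtraction option. Report anti-R0 only from its own ELISA, on the R0-monoclonal scale or in arbitrary units, which the SAP already allows.
4. State that anti-6C, anti-R0 and anti-R0.6C values are not added, subtracted or expressed as shares of one another.
5. Add a caveat that between-arm or over-time ratios of anti-R0.6C depend on the R0:6C mix, and that a pooled-serum reference would change the unit without removing this.

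The cost is a few lines of text, with no new samples or assays. The small downside is that anti-R0.6C is no longer presented as an absolute mass concentration.

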Rationale: Malaria, a disease caused by *Plasmodium* parasites, is one of the most important infectious diseases worldwide. After a period of success in global malaria control, progress has stalled in 2015-2018. The availability of a transmission blocking vaccine would be a critical step to move towards malaria elimination[1, 2]. The R0.6C fusion protein, consisting of the N-terminal region of Glutamate Rich Protein GLURP (R0) and the 6-cysteine C-terminal fragment of the well-established Pfs48/45 antigen (6C), is a lead candidate for a transmission blocking vaccine.

Objectives

Primary safety objective:

- 1) To evaluate safety of R0.6C immunizations in healthy malaria-naïve volunteers in four dose-adjuvant combinations.

Primary efficacy objective:

- 1) To assess transmission reducing activity (TRA) to mosquitoes in the standard membrane feeding assay of sera after full course of R0.6C immunizations in each of the four dose-adjuvant combinations.

Secondary safety objective:

- 1) To evaluate tolerability of R0.6C immunizations in healthy malaria-naïve volunteers in four dose-adjuvant combinations.

Secondary efficacy objectives:

- 1) To assess the dynamics of TRA in the standard membrane feeding assay of sera collected during and after R0.6C immunizations in each of the four dose-adjuvant combinations.
- 2) To assess the dynamics of anti-6C antibody quantities during and after R0.6C immunizations in each of the four dose-adjuvant combinations.

Exploratory objectives:

- 1) To assess transmission blocking activity (TBA) in the standard membrane feeding assay in each of the four dose-adjuvant combinations.
- 2) To estimate antibody decay rate against the 6C fraction of R0.6C following R0.6C immunizations for each of the four dose-adjuvant combinations.
- 3) To quantify antibody quantities against R0.6C and the R0 fraction of R0.6C after immunization with R0.6C in each of the four dose-adjuvant combinations.
- 4) To analyse cellular immune responses after R0.6C immunization.

- 5) To compare TRA between the two dose groups (30 or 100µg R0.6C) and/or between adjuvant groups (alhydrogel and alhydrogel+Matrix-M).
- 6) To compare anti-6C antibody quantities between the two dose groups (30 or 100µg R0.6C) and/or between adjuvant groups (alhydrogel and alhydrogel+Matrix-M).

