7. INVESTIGATIONAL PRODUCT

7.1 Name and description of investigational product(s)

The R0.6C fusion protein is a chimera consisting of the 6-cysteine C-terminal fragment of PfS48/45 (6C) coupled to the N-terminal region of asexual stage Glutamate Rich Protein GLURP (R0) produced in *Lactococcus lactis* (Singh et al. 2020, Singh et al. 2017; Singh et al. 2015). The carrier protein R0 helps to enhance the immune response against PfS48/45 (Theisen et al. 2014). R0.6C and the position of the PfS48/45-6C domain is shown in Figure 1.

[figure not shown]

Figure 1: Schematic representation of PfS48/45 and the fragment that is cloned in the R0.6C fusion protein

The recombinant R0.6C protein is formulated in 10 mM HEPES, 2.5% glucose, 0.5 mM EDTA, 155 mM NaCl and absorbed to 1.6 mg/mL Alhydrogel [Al(OH)₃], at a fill volume of 0.8 mL in a 2 mL borosilicate glass vial and stored at 2-8°C.

Alhydrogel [Al(OH)₃] is an aluminium hydroxide adjuvant supplied by Croda (Denmark, USA). It has been used as a vaccine adjuvant to enhance immune responses to vaccines. The final aluminium composition in the R0.6C/Alhydrogel product is 0.8 mg/mL Aluminum.

Matrix-M is a saponin based adjuvant manufactured by Novavax (Sweden). The saponin-based Matrix-M improves immune responses and enables vaccine dose-sparing. Matrix-M is supplied ready-to-mix as a refrigerated solution (stored 2-8°C) at a concentration of 0.375 mg/mL and a fill volume of 0.75 mL. Although it is not yet fully understood how the Matrix-M adjuvant achieves its stimulatory effects, this adjuvant is known to transiently enhance the number of activated immune cells in the draining lymph nodes which may in turn lead to increased uptake and presentation of vaccine antigens to elicit a competent immune response (Reimer et al. 2012). Specifically, it has been shown that there is an increase of CD169+ macrophages, as well as activated dendritic cells, to the draining lymph nodes after immunization with Matrix-M adjuvanted vaccines, which may help to increase antigen presentation (Magnusson et al. 2018). Hence, CD169+ macrophages has previously been shown to have a role in transporting antigens to B lymphocytes by trapping them in the draining lymph node and to facilitate cross-presentation of the antigen to CD8+ T lymphocytes (Gray and Cyster 2012; Carrasco and Batista 2007). This may lead to increased humoral and cellular immune responses, manifested by cross-reactive antibodies and multi-

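### The SAP's optional subtraction for anti-R0 antibody (exploratory Endpoint 8) uses measured R0 as its own input and does not return anti-R0

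*SAP*

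**What the plan says.** The SAP, under Efficacy outcome analyses, sets out the antibody measurements in two bullets.

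- Antibodies to Pfs48/45-6C and to R0.6C are measured by ELISA and expressed in µg/mL "using humanized monoclonal antibody TB31F as a reference/standard".
- For R0, the main method is direct: "The R0 antibody prevalence and density will be determined by ELISA", in µg/mL, "using R0 monoclonal antibody as a reference/standard". Two alternatives follow. One is to report arbitrary units. The other is that "R0 antibody densities may be estimated by subtracting measured R0 antibody levels from R0.6C antibody levels".

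The R0 bullet is tagged to Endpoint 8, which the SAP lists as exploratory: "The anti R0.6C and anti-R0 antibody quantity in volunteer sera collected at different time points".

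Two facts from the protocol bear on this. Its Summary describes the vaccine antigen as "consisting of the N-terminal region of Glutamate Rich Protein GLURP (R0) and the 6-cysteine C-terminal fragment" of Pfs48/45, so R0.6C has two parts, R0 and 6C. Section 2.1.2 describes TB31F as "a monoclonal antibody TB31F against the same PfS48/46 6C region", so the standard used for R0.6C is a 6C-region antibody.

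Protocol section 13.1(i) says that anti-6C, anti-R0 and anti-R0.6C will all be measured by ELISA, but gives no subtraction. The SAP sentence is the only definition of it.

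**The concern.** A subtraction method for anti-R0 should start from the response to the whole fusion protein and remove the part that is not R0. The SAP removes R0 itself. An analyst who can apply the rule already holds the measured R0 level, and the rule turns it into something else.

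If the option were taken literally, the figure reported as anti-R0 would be a different quantity. At equal R0.6C it would also move in the wrong direction, falling as true anti-R0 rises, so groups or time points could be ranked in reverse. An analyst who noticed the problem and substituted 6C without comment would be departing from the written plan.

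The two terms are also read against different standards: R0.6C against TB31F and R0 against an R0 monoclonal. Sharing the unit µg/mL does not put them on a common scale, and the SAP states none for the subtraction.

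**Working it through.** The documents give no numerical value for this estimator, so there is no planned figure to reproduce. The check is algebraic. Let A be the R0.6C level, B the R0 level and C the 6C level.

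**1. Circularity, with no assay assumption.** The rule is B(est) = A − B. It equals B only if A − B = B, that is, if A = 2B. In every other case it contradicts the measured R0 value that was put into it.

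**2. What the difference represents.** Assume additive levels on one scale, A = B + C. This is an assumption; the documents do not state it. Then A − B = C, the anti-6C part.

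**3. Size under that assumption.** The documents give no split of the antibody response, so the share of B is varied with A = 100:

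| True anti-R0 (B) | SAP rule (100 − B) | Rule ÷ truth |
|---|---|---|
| 10 | 90 | 9.0 |
| 25 | 75 | 3.0 |
| 30 | 70 | 2.33 |
| 50 | 50 | 1.0 |
| 70 | 30 | 0.43 |
| 76.7 | 23.3 | 0.30 |
| 90 | 10 | 0.11 |

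The 76.7 row borrows the R0 share of the protein given in Protocol section 7.3. That is not a share of the antibody response and serves only as one more illustrative point.

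**4. Ordering of groups.**

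- Equal R0.6C of 100, true anti-R0 of 60 and 80: the rule gives 100 − 60 = 40 and 100 − 80 = 20. The order is reversed.
- Constant R0 share of 70%, R0.6C of 100 and 200: true anti-R0 is 70 and 140, and the rule gives 30 and 60. The order is kept, but both values are 30/70 = 0.43 of the truth.

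Reversal is therefore possible but not inevitable.

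**5. Different standards.** Suppose the R0 standard reads k times the TB31F scale, with A = 100 and true anti-R0 = 60. The rule gives 100 − 60k:

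- k = 0.5: 100 − 30 = 70
- k = 1: 100 − 60 = 40
- k = 2: 100 − 120 = −20

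The values of k are assumed. They show that the result depends on a calibration that the SAP does not specify and that it can be negative.

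**6. The likely intended rule.** Under the same additivity, A − C = B. With A = 100 and C = 75, 50, 23.3 and 10, this returns 25, 50, 76.7 and 90, the true anti-R0 in each case. Both terms are also read against TB31F.

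**The case against.** The strongest reply is that this is a one-word slip and not a faulty method. Anyone applying the rule would already have measured R0 in hand and would see the problem at once. The main route is a direct R0 ELISA, the subtraction is optional, and it serves only part of an exploratory endpoint. The illustrative sizes rest on assumed inputs: the 9-fold figure follows from choosing 10 and 90 as end points, and rank reversal needs roughly equal R0.6C across groups, which two doses and two adjuvants may not give. If 6C was the intended subtrahend, the mismatch of standards largely disappears, because 6C and R0.6C share TB31F.

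Most of this stands, and it limits the weight of the point. The numbers illustrate the algebra and do not estimate an effect in this trial. Rank reversal is one scenario among several. The standards argument applies to the rule as printed more than to the probable intention.

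The reply does not rescue the sentence. Circularity needs none of those assumptions, no other section redefines the subtraction, and being optional does not make the formula valid.

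**Conclusion.** The point holds, as a minor one. The subtraction in the SAP is circular as written and does not return anti-R0 except when R0.6C is exactly twice R0. That conclusion needs no assumption. The further reading, that the result is mainly anti-6C, rests on additive levels on a common scale, which the documents do not state.

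The size and direction of any error in this trial cannot be known, because neither document gives the anti-R0/anti-6C split. The reach is narrow: only the anti-R0 half of Endpoint 8, and only if this alternative is used. Anti-R0.6C, anti-6C, TRA and all safety endpoints are unaffected. That 6C was the intended subtrahend is an inference from the antigen's structure and the shared standard, and the authors need to confirm it.

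**What to change.** The authors should say which level was meant to be subtracted.

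- **If it was 6C:** replace R0 with Pfs48/45-6C as the level subtracted from R0.6C. State the assumptions of additivity and a common scale, and how negative differences will be handled. Report the result in TB31F-equivalent or arbitrary units, note that TB31F targets 6C, and keep these values apart from those read against the R0 monoclonal.
- **Otherwise:** delete the subtraction and rely on the planned R0 ELISA, in µg/mL or arbitrary units.

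The essential change is one SAP sentence, corrected or removed; the first route adds a short statement of assumptions. The 6C, R0.6C and R0 ELISAs are already planned, so no new assay is needed.

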Because the mode of action of TBVs is so explicit, there is a highly informative endpoint in the SMFA that is a clear indicator of later public health impact. For other vaccines, there is no such clear in vitro assay. The TRA measured in the SMFA assay around which there is confidence that blocking activity is present was set by consensus at 80% reduction in oocyst intensity, however even TBVs with a TRA of less than 80% could eliminate plasmodium at low transmission levels over consecutive transmission seasons[10].

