### Estimation of empirical power for an analysis of transmission reducing activity under different assumptions

#### The simulation algorithm

1. We generate  $n_0$  subjects in the control (pre-treatment) group and  $n_1$  subjects in the treatment (post-treatment) group with a variable  $x_i$  to indicate whether the subject is in the control group ( $x_i = 0$ ) or in the treatment group ( $x_i = 1$ ).
2. We generate  $m$  mosquito dissections for each subject.
3. We simulate subject-specific random intercepts ( $z_i$ ) from a normal distribution with a mean of 0 and a specified standard deviation  $\sigma$ , i.e.  $Z \sim N(0, \sigma)$ .
4. Lastly we generate the oocyst counts ( $y_{ij}$ ) for each subject  $i$  and mosquito  $j$  using a negative binomial distribution such that  $Y \sim NB(\mu, \theta)$  where  $\theta$  is the anticipated dispersion parameter and  $\mu_{ij} = \exp(\beta_0 + \beta_1 x_{ij} + z_i)$  where  $\beta_0$  is the anticipated mean of the log oocyte counts in the control group and  $\beta_1$  is the anticipated regression coefficient used to estimate the TRA, such that

$$\beta_1 = \log\left(1 - \frac{TRA}{100}\right).$$

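### The optional count of individuals with statistically significant TRA could far exceed its nominal 2.5% error rate, unless the individual-level model carries a feed-level variance term that the SAP does not state

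*SAP*

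**What the plan says.** The relevant text is in the SAP, Efficacy outcome analyses.

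- **Assay unit and comparator.** TRA is the relative reduction in oocyst intensity from "one feeder per test sample) compared to baseline serum controls". On replication: "Samples may be tested in one or two independent SMFA experiments". No rule says which samples get a second experiment. For TRA the SAP does not say whether the baseline is the person's own or pooled; for TBA it allows a pooled baseline.
- **Model.** "TRA values for each participant and time-point will be estimated using generalized linear models, as previously described", with a literature citation. The condition placed before this is "If significant transmission reduction is measured". No feeder or experiment term is mentioned. For antibody data, by contrast, the same section names mixed models with random intercepts.
- **Summaries.** "We may calculate the percentage of individuals per group that have at least 50%, 80% and 90% TRA at relevant timepoints", and also "the percentage of individuals per group with statistically significant TRA at relevant timepoints". Both are optional and are tagged to Endpoint 10, which is exploratory.
- **Error rate.** Confidence intervals and P values sets a two-sided 0.05 level and leaves multiplicity adjustment to judgement. No false-positive rate is given for individual calls.

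The power model (Protocol 5.4.1; SAP, The simulation algorithm) does carry variation beyond the mosquito level. "We simulate subject-specific random intercepts", it says, with SD 0.64 on the log scale, drawn independently for each pre-treatment and post-treatment unit. The simulated data are then analysed with a mixed model.

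**The concern.** With one feeder per sample, a single participant's data cannot separate the effect of the serum from the chance level of that feed. A model whose only error is the spread among about 20 mosquitoes treats any difference between two feeders as a serum effect. The power calculation allows for variation between units and the individual test, as described, does not.

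There are 8 participants per dose-adjuvant group and no placebo group. A percentage of individuals with significant TRA is easy to quote from a proof-of-concept trial, and a few chance calls in 8 could make an inactive arm look active.

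**Working it through.** **Inputs.** Mosquitoes per sample m = 20; log mean oocyst count 3.7037, so mean exp(3.7037) = 40.6; dispersion 4.451; random-intercept SD 0.64, so variance 0.4096 (Protocol 5.4.1; SAP, Simulation results). Two-sided 0.05, so 2.5% in the direction of a reduction.

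**Not given in the documents, so varied.** The share f of the 0.4096 that varies between feeds of the same person, and whether the TRA baseline is own or pooled.

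**1. Reproducing the plan's figure.** Sampling variance of one feeder's log mean: (1/40.6 + 1/4.451)/20 = 0.01247. SD of a unit's log mean: sqrt(0.4096 + 0.01247) = 0.650. For 75% TRA with n0 = 10 and n1 = 8, SE = 0.650 × sqrt(1/10 + 1/8) = 0.308 and ln 4/0.308 = 4.50. Power = Φ(4.50 − 1.96) = 99.4%, against 99.8% in the table. For 8 against 8, which is not tabulated, the same formula gives 98.9%. Some 25% and 50% TRA cells differ from this approximation by up to about 6 points.

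**2. What a mosquito-only test sees.** SE of one pre/post log ratio = sqrt(2 × 0.01247) = 0.158. An observed reduction of 1 − exp(−1.96 × 0.158) = 27% is then significant.

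**3. No vaccine effect, own baseline, one experiment.** The true variance of the log ratio is V = 2(0.4096f + 0.01247). The chance of a significant reduction is Φ(−1.96 × 0.158/√V). The chance of reaching cut-off c is Φ(ln(1 − c)/√V).

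| f | feed SD | √V | significant | expected in 8 | TRA ≥50% | ≥80% | ≥90% |
|---|---|---|---|---|---|---|---|
| 100% | 0.64 | 0.919 | 36.8% | 2.9 | 22.5% | 4.0% | 0.6% |
| 50% | 0.45 | 0.659 | 31.9% | 2.6 | 14.7% | 0.7% | <0.1% |
| 25% | 0.32 | 0.479 | 25.9% | 2.1 | 7.4% | <0.1% | about 0 |
| 10% | 0.20 | 0.327 | 17.2% | 1.4 | 1.7% | about 0 | about 0 |
| 0% | 0 | 0.158 | 2.5% | 0.2 | about 0 | about 0 | about 0 |

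Simulated negative binomial fits with estimated dispersion (3,000 per row) gave 37.2%, 31.5%, 26.7%, 17.5% and 3.0% significant. At 36.8%, the chance of at least one false call in 8 is 1 − 0.632^8 = 97%.

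**4. Pooled baseline, taken as error-free, one experiment.** Person effects no longer cancel, so the split does not matter. √V = sqrt(0.4096 + 0.01247) = 0.650 and the model SE is sqrt(0.01247) = 0.112. The significant rate is Φ(−1.96 × 0.112/0.650) = 36.8%. TRA of at least 50% occurs in Φ(−0.693/0.650) = 14.3%, and of at least 80% in 0.7%.

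**5. Two experiments, feed term still omitted.** With own baseline, the true and the assumed variance both halve, so the significant rate stays at the step 3 values (36.8% at f = 100%). At f = 100% the 50% cut-off improves from 22.5% to 14.3%. With a pooled baseline the significant rate is 36.8% to 40.5%, depending on f.

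**6. Feed term included.** The rate returns to 2.5%. At f = 100% with own baseline, the reduction needed for individual significance becomes 1 − exp(−1.96 × 0.919) = 83.5% with one experiment and 1 − exp(−1.96 × 0.919/√2) = 72% with two.

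**The case against.** **The model is in a source that is not reproduced here.** The SAP defers to a cited method and, in Statistical Software, names an online analysis tool. If either includes a feed-level term, the inflation shrinks. This stands, and it makes the point conditional. The SAP should then state the term.

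**The 0.64 is described as subject-specific.** Any part that is a stable trait of the person cancels against that person's own baseline, and with no feed-level part the rate is the nominal 2.5%. This stands for an own baseline. It does not help with a pooled baseline.

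**Individual TRA is estimated only after significant reduction is found.** This limits the case where nothing works anywhere. But the level of that condition (group or individual) is undefined, and passing it does not control the error for each participant.

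**The summary is optional and exploratory.** This stands. The primary efficacy endpoint is a within-group comparison, and in the bullet concerned the between-group comparison is attached to mean TRA, not to these percentages.

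**Two stronger readings are tempting.** A reader might infer that the 50% cut-off would also label many unaffected participants. The documents do not support that: the rate runs from about 0% to 23% according to a split they do not give, and the SAP lists 80% and 90% beside it. A reader might also infer that 80% should be the sole responder criterion, because confidence in blocking activity "was set by consensus at 80% reduction in oocyst intensity". The same sentence in Protocol section 1 goes on to say that TRA below 80% could still matter where transmission is low, so the lower cut-off has a use.

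**Conclusion.** The point holds for the individual significance count, conditionally. If the generalized linear model has no feeder or experiment variance term, the nominal 2.5% becomes 17% to 37% with own baseline once a tenth or more of the 0.64 variance lies between feeds, and about 37% with a pooled baseline. That is roughly 1.4 to 2.9 false calls in a group of 8, against 0.2 at the nominal rate. A second experiment alone does not correct it. The 50% percentage is affected less, and the 80% and 90% percentages little (4% or less).

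This rests on the plan's planning values carrying over to this trial, on 20 mosquitoes per feeder, and on log-normal variation between feeds. It does not show that the primary endpoint is compromised. Because the summary is optional and exploratory, the correction is of low to moderate priority.

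**What to change.** Do not report the significance count from a mosquito-level model. Choose one of these:

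1. Delete it.
2. Base it on a model with a feed or experiment variance term, estimated from samples run in two experiments.
3. If there are no replicate feeds, use the spread of individually fed I1-1 sera. Label it a conservative bound, because it also contains person-to-person variation.

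State in the SAP whether the TRA baseline is own or pooled, and which variance terms the individual model contains.

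Keep the 50%, 80% and 90% percentages as descriptive results with exact 95% confidence intervals per group. Where I1-1 sera are fed individually, show beside them how often I1-1 sera meet each cut-off. If the trial uses own baselines, note that comparing different people's I1-1 sera tends to overstate the false rate.

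The cost is SAP wording and a short calculation. It uses data already generated if samples are replicated or I1-1 sera are fed individually. The downside is fewer participants counted as significant and wider individual intervals.
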